13.3. Data analysis and reporting

The data will be collected from each center in the electronic Case Report Form (eCRF) data base via Oracle Clinic. A specific account number will be given to each center to access the system from any internet-enabled computer. Access to Internet is required for the sites to enter data into the system. User Identification codes will be created to identify data input from each center. The clinical data will be entered by the study staff and transmitted to the central database in an anonymous format so that the study sponsor will not be able to identify the patient, in accordance with the Chinese Data Privacy Directive. Electronic automatic and manual queries will be generated for missing, incorrect or doubtful data and sent directly to the study center via Oracle Clinic.

All the detailed data analyses are described in the Statistical Analysis Plan (SAP). Any change to the data analysis methods described in this section and/or the SAP will require an amendment only if it changes a principal feature of the study description. Any other changes to the data analysis methods will be described and justified in the Final Report or publication.

Based on the clinical practice in the surgery procedures and number of subjects enrolled per center, an investigation of center effect will be investigated including an independent variable for center in the model as well as summary statistics if needed.

13.4. Analysis of Clinical Data

Patient demographics and baseline characteristics will be presented using appropriate summary statistics. This includes mean and standard deviation, minimum, maximum and median with the interquartile range [IQR] for continuous variables, and counts and percentages for categorical variables. Summary statistics will be reported with maximum 2 decimals, as appropriate. The SAS software (SAS Institute Inc., Cary, NC, USA) or any other validated Statistical Software will be used to perform statistical analyses. The test for a treatment effect corresponds to showing that the upper bound of the two-sided 95% confidence interval (equivalent to the lower bound of a one-sided 97.5% confidence interval) for $\mu_E(t) - \mu_C(t) < \text{margin}$. Graphical representations will be used as deemed appropriate. No adjustments for multiple comparisons or multiple look at data will be performed. Outliers and influential observations will be identified via graphical plots and according to study team decision and the analysis could be repeated excluding potential outliers. In case of missing data, the imputation of missing data will be performed using the most appropriate method depending on the pattern of missing in the data and the type of the imputed variable. After the imputation of the missing values the models will be rerun.

The data will be analyzed according to the intention-to-treat principle and a Full Analysis Set (FAS) will be used for primary final analysis. The FAS is the patient set containing all the patients included in the study that have signed the study Informed Consent and have received the study treatment. A secondary analysis could be performed on a Per Protocol Set (PPS). The PPS patients set containing all the patients that meet the inclusion/exclusion criteria with no other major protocol deviation that

could impact the clinic outcomes and have the 6 months follow-up visits completed. Any patient who does not satisfy the inclusion/exclusion criteria or receives the wrong treatment will be eliminated from the per-protocol population. Details of endpoints analyses and additional analysis will be described in the Statistical Analysis Plan.

The analyses based on freedom from event at 6 months will be described by means of Kaplan-Meier curves. Cox models will be fitted and hazard ratios (HRs) with 95% confidence intervals will be computed. The proportional hazard assumptions will be tested by means of Schoenfeld residuals. The exposure time (months) will be computed from the date of the index procedure to the date of the last available follow-up or date of first event: [(data end – data in)/30.4].

The rate of event will be computed and reported separately for each group, together with their 95% confidence intervals. Rates were compared by means of either a mixed Poisson model or a negative binomial regression model (if over dispersion was present). Incident rate ratios (IRRs) and 95% confidence intervals were used to compare the two groups.

Analysis of endpoints based on comparisons between groups on continuous measurements will be performed by Student's t-test or non-parametric test (Mann-Whitney U test) for normal and non-normal distributions, respectively. Normality will be assessed by means of Shapiro-Wilks test and the p-value will be reported. Categorical variable parameter comparisons will be performed using a Chi-square test, or a Mantel-Haenszel test for trend for ordinal variables with 3 or more categories.

The analysis on the first primary endpoint based on NRS will use one measure per patient and the comparison will be between the average NRS in both groups. It will be claimed that XPEDE is not inferior to MENDEC with respect to NRS score if the upper bound of the two-sided 95% confidence interval of the difference ($\mu_X(t) - \mu_M(t)$) is less than the margin.

The analysis on the second primary endpoint based on Index Vertebral Body Angles will use multiple data points per patient according to the number of levels treated. Assuming not completely independence among measures within same patient the analysis will be performed by means of Generalized Estimating Equation (or mixed models for repeated measures) using patient as the subject. The model will have the Index Vertebral Body Angles as dependent variables and baseline value, number of level treated (as the multiple data points) and arm as explanatory variables. All assumptions for regression models will be assessed by viewing plots of the residual values. It will be claimed that XPEDE is not inferior to MENDEC with respect to Angulation if the upper bound of the two-sided 95% confidence interval of the difference ($\mu_X(t) - \mu_M(t)$) is less than the margin.

The overall study is considered reached if both the null NI hypotheses are rejected. A separate Statistical Analysis Plan (SAP) will be developed prior to data being analyzed to further describe statistical methods, pre-specified data handling rules, and pre-specified analyses that will be included in the final study reports. Any deviation from the pre-specified statistical analyses will be noted in the study report.

The Statistical Analysis Plan will include a comprehensive description of the statistical methods and analyses to be included in reports that include analysis of endpoints. Any change to the data analysis methods described in the CIP will require an amendment only if it changes a principal feature of the CIP. Any other change to the data analysis methods described in the CIP, and the justification for making the change, will be described in the clinical study report.

14. Ethics

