5.2.2. Secondary Endpoints(s)

The secondary endpoints include:

- Change of NRS score from baseline at 1 day and 3 months
- Change of ODI from baseline at 1 day, 3-month visit and 6-month visit.
- Change of SF-36 from baseline at 1 day, 3-month visit and 6-month visit
- Change in Vertebral body height restoration at 1 day and 3-month visit and 6 month
- Change in Vertebral body Angles from baseline at 1 day, 3-month visit
- Adverse event through 6-month visit, in particular, the following events will be reported:

- Bone Cement Implantation Syndrome;
- Bone Cement leakage;
- Vertebral body compression fracture;
- Adjacent vertebral body fracture;

6. Study Design

The Xpede Study is a prospective, 1: 1 randomized, single blinded, multi-center human clinical trial designed to confirm the safety and efficacy profile of the Kyphon®Xpede™ Bone Cement for regulatory approval in China. This study will enroll up to 180 subjects in order to demonstrate that the Kyphon®Xpede™ Bone Cement is non-inferior to the Mendec Bone Cement by more than a small pre-specified amount in terms of the primary endpoint. This amount is defined as the non-inferiority margin (section 13 for details). Subjects will be randomly assigned with a 1:1 ratio to the Kyphon®Xpede™ Bone Cement arm or to the Mendec Bone Cement arm and then followed for a duration of 6 months in all sites. All study sites will be in China. All study sites and Investigators are provided under a separate cover.

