9.3. Stratification and Treatment Assignment

Randomization will be performed according to a randomization schedule developed by the sponsor or sponsor's representative after the subject has signed the Informed Consent and prior to the surgical procedure. The clinical database will contain the randomization distribution system which will be used for this study.

Individuals who are randomized and receive the study treatment will be considered study (treated) subjects; only data from study (treated) subjects will be included in endpoint analysis.

Patients will be randomized 1:1 to either Xpede™ Bone Cement or Mendec bone cement. The sequence of treatments will be randomly permuted in blocks of 2 or 4 patients per block. The blocked randomization will be centralized and schedules will be created by the study statistician using statistical software. The randomization will be performed by the center via the EDC system (Oracle Clinic). To minimize the selection bias, the randomization procedure for this study will use the site (3 sites), the number of vertebral to be treated (1,2 or 3) and the type of procedure (2 procedure: VP and BKP) as stratification factors, so that there will be a separate permuted block randomization list for each stratum (18). This guarantees treatment balance within strata.

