13.1.2. Sample Size Calculations

Sample size calculations were performed in SAS software (SAS Institute Inc., Cary, NC, USA). A sample size is determined such that the non-inferiority of the primary objective is demonstrated that results are not appreciably worse in XPEDE arm compared to MENDEC Spine arm. Based on this information the assumptions for the sample size are:

¹¹ Gemma Marcucci, Maria Luisa Brandi. Kyphoplasty and vertebroplasty in the management of osteoporosis with subsequent vertebral compression fractures. Clinical Cases in Mineral and Bone Metabolism 2010; 7(1): 51-60

¹² Maiettini D., Orgera G., Bisaccia M., Piscitelli L., Laurino F., Meccariello L., Rebonato S., Schiaroli E., Rossi M. and Rebonato A.. Percutaneous Vertebroplasty Improves Pain Control and Quality of Life in Patients Suffering from Back Pain: A Single Center Experience.

¹³ Feng C., Yong-Hui X., Wen-Zhen C., Wei S., Yang G., Bo F. and Difei W. Percutaneous kyphoplasty for the treatment of spinal metastases. ONCOLOGY LETTERS 11: 1799-1806, 2016

¹⁴ Dohm M, Black CM, Dacre A, Tillman JB, Fueredi G; KAVIAR investigators. A randomized trial comparing balloon kyphoplasty and vertebroplasty for vertebral compression fractures due to osteoporosis. AJNR Am J Neuroradiol. 2014 Dec;35(12):2227-36.

- The NRS score which ranges from 0 to 10 is assumed to be approximately normally distributed.
- The NRS score is to be assessed at 24 weeks (6 months) after the procedure.
- The NRS at 24 weeks (6 months) is expected to be 3.5 in the MENDEC Spine treatment, and 3.5 or more in the Xpede. A difference in NRS score of 1.5 or less is considered clinically unimportant for this comparison¹⁵. It is considered the maximum acceptable increase in NRS score compared to the MENDEC Spine arm.
- The standard deviation of the NRS score is expected to be approximately 3.27 (the highest value from the literatures sited above) for each treatment. Common standard deviation will be assumed for both arms.
- The sample size should be sufficient to produce an 80% chance (power) of a significant result at a one-sided 0.025 significance level.

The non-inferiority margin "m" that characterizes the largest absolute difference considered to be dismissible is defined as 1.5. Since smaller values of NRS are better, the hypotheses are based on lower-tailed test:

$$H_0: \mu_X(t) \geq \mu_M(t) + m \quad \text{vs} \quad H_A: \mu_X(t) < \mu_M(t) + m$$

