Where: t is 24 weeks (6 months), μ_X is the NRS mean score in the Xpede arm, μ_M is the NRS mean score in the MENDEC and "m" is the non-inferiority margin.

Based on this statistical test and assuming a one-sided type I error rate of 0.025 and a type II error rate of 0.20 or equivalently, power of 0.80 for the final analysis, it will be claimed that Xpede is not inferior to MENDEC with respect to NRS score if the upper bound of the two-sided 95% confidence interval of the difference ($\mu_X(t) - \mu_M(t)$) is less than the margin.

Thus, the non-inferiority hypothesis will require a sample size of 152 (76 per arm) subjects and including 15% of potential loss-to-follow-up, the total sample size for the study will be 179. If we use 3 * 3 * 2 strata, the sample size should be 180 to be divisible of 18 (90 per arm).

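### Adverse events are compared between arms only by hazard ratio, rate ratio and chi-square test, which break down when an arm has few or no events; no risk difference is planned

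*Protocol*

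**What the plan says.** Protocol 13.4 (Analysis of Clinical Data), repeated in part in the synopsis, gives these tools for events:

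- **Described per arm:** Kaplan-Meier curves for freedom from event at 6 months, and each group's event rate with a 95% CI. The interval method is not named.
- **Compared between arms:** "Cox models will be fitted and hazard ratios (HRs) with 95% confidence intervals will be computed". For rates, from a mixed Poisson or negative binomial model, "Incident rate ratios (IRRs) and 95% confidence intervals were used to compare the two groups". For categorical variables, a chi-square test.

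No risk difference, exact test or rule for sparse or zero counts is given.

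Protocol 5.2.2 names four adverse events for particular reporting: "Bone Cement Implantation Syndrome", cement leakage, vertebral body compression fracture and adjacent vertebral fracture. Protocol 10.1 also lists serious events seen with acrylic cements, including cardiac arrest and pulmonary embolism.

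The SAP repeats the chi-square test (7.2) and the four named events (4.2). The secondary-endpoint models in 7.9.2 cover only NRS, ODI, SF-36, height and angle. Safety (7.10) consists of adverse event tables by system organ class and preferred term, the same by relationship to bone cement, and listings. It names no hazard ratio, rate ratio or confidence interval. The table mock-ups (10.1) are a separate document and were not available.

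**The concern.** The synopsis states the purpose as showing Xpede non-inferior to Mendec in safety as well as efficacy, and the trial is meant to support registration in China. Each primary efficacy endpoint is judged on a between-arm difference with a confidence interval. Safety has no such measure. Its between-arm estimates are both ratios, and a ratio depends on having events in both arms.

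If some of the named harms are uncommon, an arm of 90 may well record none. The fitted hazard ratio or rate ratio then runs to 0 or infinity, or does not exist, and the chi-square p-value rests on expected counts too small for it. The data would still limit how much extra risk Xpede could carry, but no planned analysis would express that limit as a comparison of the two cements.

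**Working it through.** **Inputs.** From protocol 13.1.2: one-sided alpha 0.025, power 0.80, NRS margin 1.5, SD 3.27, 15% loss, 90 per arm. From protocol 9.3: 1:1 allocation. Event risks are not in the documents; a range of 0.5% to 5% is assumed, equal in both arms.

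**The plan's own figure.** No event endpoint has a sample-size calculation, so the figure to reproduce is the one that yields 90 per arm. The normal formula gives 2 × (1.960 + 0.842)² × 3.27² / 1.5² = 74.6, so 75 per arm. The noncentral t gives 76 per arm (power 0.802), or 152 in total. Then 152 / 0.85 = 178.8, so 179, rounded to 180 as a multiple of 18. The figures of section 13.1.2 reproduce.

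**Chance of an empty arm.** With true risk p and n per arm, P(no events in an arm) = (1 − p)ⁿ. So P(at least one arm empty) = 1 − [1 − (1 − p)ⁿ]², and P(both empty) = (1 − p)²ⁿ. At p = 1% and n = 90: 0.99⁹⁰ = 0.405; 1 − 0.595² = 0.646; 0.405² = 0.164. An arm with no events also has no patients with an event, so this applies to the hazard ratio and the rate ratio alike.

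| Assumed risk | One arm empty or both, n = 90 | Both empty, n = 90 | One arm empty or both, n = 76 |
|---|---|---|---|
| 0.5% | 86.8% | 40.6% | 90.0% |
| 1% | 64.6% | 16.4% | 71.5% |
| 2% | 29.8% | 2.6% | 38.4% |
| 3% | 12.5% | 0.4% | 18.8% |
| 5% | 2.0% | <0.1% | 4.0% |

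The n = 76 column is the evaluable number after 15% loss.

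**What the planned tools return, Xpede vs Mendec.**

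- *Ratios, 3 vs 0 events.* The estimate is infinite and the usual Wald interval fails. An exact conditional interval with equal exposure keeps a lower bound: 0.025^(1/3) = 0.292, and 0.292 / 0.708 = 0.41, so 0.41 to infinity. For 0 vs 3 it is 0 to 2.42.
- *Ratios, 0 vs 0 events.* Undefined by any method.
- *Chi-square, 3/90 vs 0/90.* The expected count is 1.5 events per arm. The statistic is 2 × 1.5²/1.5 + 2 × 1.5²/88.5 = 3.05, p = 0.081. Fisher's exact p = 2 × C(90,3)/C(180,3) = 2 × 117,480/955,860 = 0.246.
- *Per-arm interval, 0/90.* A Wald interval has zero width. Clopper-Pearson gives 0 to 1 − 0.025^(1/90) = 4.0%.

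**What a risk difference returns, 90 per arm.**

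| Events | Risk difference | Miettinen-Nurminen 95% CI | Newcombe 95% CI |
|---|---|---|---|
| 0 vs 0 | 0.0% | −4.1% to +4.1% | −4.1% to +4.1% |
| 1 vs 0 | +1.1% | −3.0% to +6.1% | −3.1% to +6.0% |
| 3 vs 0 | +3.3% | −0.9% to +9.4% | −1.3% to +9.3% |
| 0 vs 3 | −3.3% | −9.4% to +0.9% | −9.3% to +1.3% |

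Both intervals are finite in every zero-event case.

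**The case against.** The strongest reply has five parts.

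1. **The plan does give absolute measures.** A reader might infer that rare harms would get no usable estimate or interval at all. The documents do not support that. Protocol 13.4 promises each group's event rate with a 95% CI, and Kaplan-Meier curves. With an exact method the per-arm interval stays informative at zero events. This part stands, and it confines the point to the comparison. Two separate per-arm intervals still do not give an interval for the difference, and the SAP's safety section does not carry them forward.
2. **An empty arm does not make a ratio worthless.** Protocol 13.4 does not prescribe Wald intervals, and an exact interval keeps one finite bound. Only 0 vs 0 is wholly undefined, which is 16% rather than 65% at a 1% risk. This also stands, but the plan names no such method.
3. **Rarity is assumed.** The documents place no named event at any particular risk. At 5% or more the problem nearly vanishes. This stands, which is why the result is given as a range.
4. **The event models are described generically.** Protocol 13.4 does not tie the Cox or Poisson models to each named event, and it leaves detail to the SAP. That is true. But the SAP supplies no other between-arm estimate for them, so on either reading no absolute comparison is planned.
5. **No success criterion depends on it.** Success rests on the two efficacy hypotheses, and no safety margin is set. This stands and limits the consequence to how the safety evidence can be read.

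**Conclusion.** The point holds for the between-arm comparison. The protocol's only tools for comparing events are a hazard ratio, a rate ratio and a chi-square test, and the SAP's safety section drops the ratios and intervals. If a named event has a true risk of about 1% or less, with 90 per arm and equal risks, at least one arm is empty 65% of the time or more; the figure is 30% at 2% and 2% at 5%. In those cases the ratio is 0, infinite or undefined, standard intervals fail, and the chi-square approximation is poor at such counts.

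This rests on assumed event risks, since the documents state none. The efficacy conclusions are unaffected. The point goes beyond missing detail, because a risk difference with a score-type interval is a workable comparison where the stated ones can fail.

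**What to change.** In protocol 13.4 and SAP 7.10, for each of the four named events and for SAEs:

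- Report the risk difference (Xpede minus Mendec) in patients with the event by the 6-month visit, with a score-type 95% CI such as Miettinen-Nurminen.
- Give the proportion in each arm with an exact (Clopper-Pearson) 95% CI.
- Use Fisher's exact test in place of chi-square when expected counts are small.
- Keep the HR and IRR as supplements, reported only when both arms have events. A penalised Cox fit is not a substitute, because with no events in either arm there is nothing to fit.

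The cost is a little more analysis work and a wording change to the SAP and protocol, with no new data. A formal protocol amendment would need the approvals listed in protocol 14.1. Protocol 13.4 requires an amendment for changed analysis methods only when a principal feature changes.

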14.1. Statement(s) of Compliance

- This study is a pre-market clinical trial for product registration. The study will be conducted in accordance with the laws and regulations of China, including any future applicable laws and regulations in China.
- To protect the rights and welfare of patients, this clinical study will be conducted in compliance with the latest version of the Declaration of Helsinki (2013), the Clinical Trial Agreement (CTA) and Clinical Investigation Plan, the laws and regulations of China including Good Clinical Practice for Medical Devices (CFDA Order No. 25), Announcement of Chinese Regulation on Filing of Medical Device Clinical Trial (2015, No.87) and also including applicable data protection laws. Sites will also comply with any additional ethics committee requirements applicable.
- The sponsor will provide the medical institution with Medical Device Clinical Trial Notice
- The principles of the Declaration of Helsinki have been implemented through the patient informed consent (IC) process, Ethics Committee approval, study training, clinical trial registration, preclinical testing, risk-benefit assessment and publication policy.
- Approval of the CIP or CIP amendments is required from the following groups prior to any study procedures at a study site: Medtronic, principal investigators and Ethics Committee. Similarly, approval of subsequent revisions to the CIP is required at each study center from the above mentioned groups prior to implementation of the revised CIP at that center.
- Sponsor should be responsible for filing the study to Shanghai Municipal Food and Drug Administration after Ethics Committee approval of the current version of the CIP and fully executed Clinical Trial Agreement.
- All products will be labelled as per local regulations in China and products requiring investigational labelling will be labelled investigational as per local regulatory requirements.
- All participating study sites and investigators should make all the study data and study related records and including source data/records available for the monitoring, audits work from sponsor and inspection from EC and/or Regulatory body per their requirements to ensure the quality of the clinical trial.
- The sponsor shall avoid improper influence on, or inducement to, the subject, monitor, any investigator(s) or other parties participating in, or contributing to, the Xpede study.

- Sponsor representatives may provide support as required for the study, including technical support at site. Sponsor representatives may provide technical support as required for the study under supervision of the Principal Investigator, including:
 - Provide study training relevant and pertinent to the involvement of personnel conducting study activities and investigator responsibilities.

Technical support will be under the supervision of a study investigator, but no data entry on the eCRF shall be performed by Medtronic personnel or their representatives at sites.

